11.7 Anti-Drug Antibodies

A summary table for IgG and Neutralizing antibody will present the number and percentage of patients who are positive or negative by visit. In case that IgG was tested twice on the same visit (for example, due to hypersensitivity) only the 1st test will be part of the summary by visit.

The decision about ADA status at each visit is based on sequential evaluation as follows:

- 1. If the IgG screening is negative then ADA at that visit is reported as "negative" (and no more evaluations).
- 2. If the IgG screening is "Presumptive Pos", the next evaluation is the IgG Immunodepletion
- a. If IgG Immunodepletion is negative then the ADA status at the visit is reported as "negative"
- b. If IgG Immunodepletion is positive then the ADA status at the visit is reported as "positive"

The table will also show for IgG and Neutralizing antibody the number and percentage of patients with their overall (i.e., throughout the study) post-treatment status where post-treatment positive is defined as positive in at least one (scheduled or unscheduled) visit post baseline (Visit 1), or negative if negative at all (scheduled or unscheduled) post-baseline visits, regardless of status at baseline.

IgE is tested in case of hypersensitivity. The table will show the number and percentage of IgE positive and negative at baseline and screening (among patients who had hypersensitivity) and the IgE post-treatment status, defined as above.

Patients are considered to be treatment emergent ADA positive if they satisfy one of the following conditions:

- 1. Titer boosted: patients who were IgG positive to their assigned treatment arm at baseline and boosted post treatment (i.e., titer increase by at least 4-fold from baseline. See Shankar et al. 2014 and FDA Guidance for Industry, January 2019: Immunogenicity Testing of Therapeutic Protein Products Developing and Validating Assays for Anti-Drug Antibody Detection).
- 2. Treatment Induced: patients who were IgG negative to their assigned treatment arm at baseline or their IgG at baseline was missing and are positive in at least one timepoint post first infusion

The number and percentage of patients who are Treatment emergent ADA (yes/no) will be presented by treatment arm. Treatment emergent status will be missing if the patient is missing all the post-baseline assessments. For treatment emergent ADA, the table will indicate to which of the two groups a patient belongs (titer boosted or treatment induced).

A shift table from ADA status at baseline (positive / negative / missing) to overall status during study (positive if positive in at least one visit post baseline, or negative if negative at all post-baseline visits or missing if missing all post baseline assessments) will be presented by treatment arm. In addition, a shift table from Baseline to Visit 53 will be presented, where only patients who have both visits will be included.

Note that only patients who tested positive for IgG ADA will be tested for ADA characterization, i.e., IgG titer, neutralizing activity and positivity to other unique PRX-102 epitopes, will be listed.

11.8 Medication

Medications reported at screening or at any point after randomization, collected in the eCRF Concomitant Medication form, will be coded by World Health Organization (WHO) Drug Dictionary 20160601E. Medications, collected at screening, whose end date was prior to first study drug intake will only be listed. All other medications will be considered concomitant medications and will be tabulated by treatment arm by medication class and standardized medication name. Medication classes will be presented alphabetically; within each medication class, standardized names will be sorted by decreasing order of PRX-102 frequency.

Listing of medications will include start and end date together with a flag to mark medications collected at screening and stopped prior to study drug treatment start.

In order to identify ACEi, ARB and pain medications taken at baseline the following rules will be considered:

- A medication whose end date was prior to first study drug intake, regardless if start date is provided or partially/completely missing, will not be considered to be taken at baseline.
- If the end date is after first study drug intake or is missing then the medication will be considered to be taken at baseline if
 - o Start date is known and was prior to first study drug intake
 - o If the month and/or day of start date are missing, and the year is earlier than the year of the 1st infusion
 - \circ If the day is missing, the year is the same year as 1st infusion and the month is earlier than the month of 1st infusion.

In all other cases, it will be assumed that the drug was taken after the 1st infusion (i.e., not taken at baseline).

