7.2.1 Partial or Missing Dates of Medication

The following imputations will be used in case of incomplete dates of agalsidase-beta treatment required for the calculation of its duration prior to the study:

- The middle of the month (i.e., 15th) will be used if only the day is missing.
- In case the year is not missing, but the month is missing, the month will be imputed to July. If the day is missing as well then it will be imputed to the 1st of July
- No imputation will be done in case the year is missing.

No imputation will be done in case of fully missing medication date.

In some of the analyses, a flag of whether a medication was used at a certain visit is needed (e.g., use of Angiotensin-Converting Enzyme Inhibitor (ACEi) or Angiotensin Receptor Blocker (ARB) treatment at baseline or usage of pain medication at baseline or in the last visit). In case that partial start date and/or end date exist, imputation will be based on the above rules and determination of the flag will be based on the imputed dates and comparison with the date of the visit of interest.

In case that the year is missing from the start date, the determination of usage of a medication at different visits will be based on the stop date of the medication. If the year of the stop date is missing, then the determination will be based on the "Ongoing" status of the medication form as follows: if the ongoing status is Yes then it is assumed that the medication was taken throughout the study (including at baseline and last visits), and if the ongoing status is No then it is assumed the medication was stopped prior to the baseline visit.

Since information on infusion premedication is collected at both the medication form and the drug administration form then determination of usage of infusion premedication at a given visit is based on a different algorithm described in Section 11.8.2.

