10.10 Pain Medication

Prior and concomitant medications reported during the study will be coded by World Health Organization (WHO) Drug Dictionary 20160601E. Pain medication will be identified based on the classification assigned by the investigator in the eCRF. Pain medications will be summarized by the count and percentage of the patients with each medication by standardized medication name within medication class. Medication classes will be presented alphabetically; within each medication class, standardized medication names will be sorted by decreasing order of PRX-102 frequency.

The number of patients who used pain medication at any time during the study will be summarized by treatment group presenting count and percentage of patients by the number of medications they used (0, 1, 2, up to the maximum, where medications with identical standard names are counted once and 0 represents patients who did not take any pain medication during the study).

The change from baseline to the last visit (scheduled or unscheduled) in the number of different pain medications used will be examined by shift tables with the following categories for the number of pain medications used: 0, 1, and 2+. The tables will be presented by treatment arm. For patients who terminated early, the table will show their shift to their last assessment prior to discontinuation. This analysis will be based on the pain medication used on the day of the baseline visit, and the day of last visit.

Section 7.2.1 provides information on handling partial or complete missing dates of pain medications.

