11.8.2 Infusion Premedication

Information on infusion premedication is collected on two different forms in the eCRF: in the concomitant medication eCRF form where the identification of medications used for that purpose is done by the classification provided by investigator. In addition, the drug administration form, collects information whether premedication was used or not in relation to each infusion (and if yes, the timing – before, during or before and during infusion).

Infusion premedication will be tabulated by treatment arm by medication class and standardized medication name. Medication classes will be presented alphabetically; within each medication class, standardized names will be sorted by decreasing order of PRX-102 frequency.

A summary table of the number (%) of patients with and without premedication use at each visit by treatment group will be derived based on the drug administration form.

A shift table, to identify how many patients changed the number of infusion premedication from baseline to Week 52 and Week 104 (or the last assessment before discontinuation) will be presented. The shift table will include the following categories: 0, 1, 2, 3+. In order to assess for each subject if any infusion premedication was used at baseline or at Week 52 or 104 or last assessment, the drug administration form at that visit will be used. If based on this form, no premedication was administered then the number of infusion premedication at that visit is 0. In case premedication administration at visit of interest is confirmed from drug administration form, the number of infusion premedication for each subject will be determined by the number of medications reported in the concomitant medications form in the eCRF, in which classification for infusion premedication is marked, and the date of the study drug infusion is within the start and end date of the premedication. Note that physician may change instructions for medication several days before the visit, so no window should be considered when comparing the dates. In case of missing or partially missing dates of infusion premedication, the following imputation rules should be considered before comparing the study drug infusion date to the medication start/end dates:

- When the start date is completely missing or the year is missing then it's assumed the medication was taken at baseline.

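### SAP 7.2.1 and SAP 11.8 give opposite baseline-use flags for ACEi/ARB and pain medication when the start year is missing and the drug is ongoing or stops after the first infusion

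*SAP*

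**What the plan says.** SAP 7.2.1 covers visit-level medication flags and gives as examples "use of Angiotensin-Converting Enzyme Inhibitor (ACEi) or Angiotensin Receptor Blocker (ARB) treatment at baseline or usage of pain medication at baseline" or at the last visit. Its rules are:

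- Partial dates are imputed and compared with the visit date. With only the day missing, the 15th is used. For a missing month: "In case the year is not missing, but the month is missing, the month will be imputed to July", and 1 July if the day is missing too.
- Start year missing: when the drug stopped is decisive (the sentence begins "In case that the year is missing from the start date, the determination of usage of a medication at different visits will be based on").
- Stop year missing as well: the Ongoing box decides. For an entry of Yes, the SAP says "if the ongoing status is Yes then it is assumed that the medication was taken throughout the study (including at baseline and last visits". For the opposite entry, it says "if the ongoing status is No then it is assumed the medication was stopped prior to the baseline visit".

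SAP 11.8 also states rules for identifying ACEi, ARB and pain medication at baseline. A drug that ended before the first infusion is not a baseline drug. If the end date is later or missing, the drug counts at baseline in three situations only: a known start date before the first infusion; an incomplete start date with an earlier year; or a missing day with an earlier month of the same year. Then: "In all other cases, it will be assumed that the drug was taken after the 1st infusion (i.e., not taken at baseline".

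Neither section refers to the other for these drugs, and Section 13 does not mention the difference. SAP 10.10 points one way for its own endpoint: "Section 7.2.1 provides information on handling partial or complete missing dates of pain medications".

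**The concern.** All three positive conditions in 11.8 need a known start year, and 11.8 never consults the Ongoing box. A drug whose start year nobody recorded, and which was not stopped before the first infusion, therefore falls to the default and is treated as begun on study. Section 11.8 covers medications reported at screening, and the protocol reviews pain medication and ACEi/ARB at the screening visit (Protocol 9.2.1). The default can therefore place the start of a drug after the first infusion when the trial's own record shows it in use weeks before.

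The outputs that use the flag are:

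- **ACEi/ARB subgroup** (SAP 7.4), used for the primary endpoint (9.6) and for UPCR (10.6). Patients not identified as users at baseline go to No. Protocol 6.2.2 excludes patients with UPCR above 0.5 g/g who are not on an ACEi or ARB, so the flag could read No for a patient whose eligibility required treatment.
- **Baseline characteristics** (8.3).
- **ACEi/ARB use at baseline and during the study** (11.8.1). The patient would look like an on-study start, although SAP 16.4 calls such changes rare and Protocol 7.9 ties initiation after randomization to Medical Director approval.
- **Pain medication shift table** (10.10), with categories 0, 1 and 2+. If baseline is set by 11.8 and the last visit by 7.2.1, a patient on one unchanged drug moves from 0 to 1.

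**Working it through.** The plan states no figure to reproduce. The check applies both rules, as written, to the same records. First-infusion dates are assumed: 20 October 2018, and 10 March 2018 for one row.

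| Record | 7.2.1: at baseline? | 11.8: at baseline? |
|---|---|---|
| 1. Start year missing, stop missing, ongoing = Yes | Yes | **No** |
| 2. Start year missing, stop date after first infusion | Yes | **No** |
| 3. Start year missing, stop missing, ongoing = No | No | No |
| 4. Start year missing, stop date before first infusion | No | No |
| 5. Only an earlier start year known, ongoing | Yes | Yes |
| 6. Start in infusion year, month missing, ongoing; infusion 20 October | Yes (1 July imputed) | **No** |
| 7. As row 6, infusion 10 March | No | No |
| 8. Start in infusion month, day missing, ongoing; infusion 20 October | Yes (15 October imputed) | **No** |
| 9. Start in an earlier month of infusion year, day missing, ongoing | Yes | Yes |
| 10. Full start date before first infusion, ongoing | Yes | Yes |

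Rows 1 and 2 conflict whatever the infusion date. Row 2 reads 7.2.1 as meaning in use up to the stop date, since it names no other criterion. Row 3 agrees on the flag but not on the reason: 7.2.1 has the drug stopped before baseline, while 11.8 has it taken after the first infusion. Rows 6 and 8 conflict only for some dates. Row 6 needs an infusion after 1 July; row 8 needs one after the 15th of the month.

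**Which rule suits row 8 for ACEi/ARB.** Protocol 6.2.2 excludes initiation or dose change in the 4 weeks (28 days) before screening. Screening is Day -30 ± 10, so Day -20 at the latest. Visit 1 is Day 1 ± 7, so Day -6 at the earliest. The shortest gap is 20 - 6 = 14 days, and 28 + 14 = 42 days. In an eligible patient, an ACEi/ARB established before screening therefore began at least about six weeks before the first infusion, which is always an earlier calendar month. A start in the infusion month is unlikely to be an established baseline drug, yet the 15th-of-month imputation can flag it as one. No such criterion applies to pain medication.

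**Size per patient.** With the planned 26 and 52 patients, one patient is 1/26 = 3.8 percentage points of the agalsidase beta arm and 1/52 = 1.9 points of the PRX-102 arm.

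**The case against.** The best defence is that the conflict is narrow and low in impact. Most of that stands:

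- A reader might infer that 11.8 turns long-standing medication in general into on-study starts. It does not. A known earlier start year is enough under both rules (row 5), so for a drug taken for years only a missing start year causes the problem.
- A reader might take the premedication rule in 11.8.2 as further evidence, since it says "When the start date is completely missing or the year is missing then it's assumed the medication was taken at baseline". But 7.2.1 announces a separate algorithm for premedication, so that difference is intended.
- For pain medication, 10.10 already points to 7.2.1, which gives the stable 1-to-1 result. The false shift arises only if 11.8 is applied at baseline; but 11.8 also names pain medication, so a programmer has grounds for either.
- The 3.8 and 1.9 points are maxima per patient, not an effect per record. A patient with three baseline pain drugs, one misclassified, stays at 2+. A patient with another properly dated ACEi or ARB stays at Yes.
- SAP 7.6.2 makes no significance claims for subgroups or secondary endpoints.

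One defence fails. Section 7.2.1 says that fully missing dates are not imputed, which might seem to leave these records unclassified. But it then sets the flag from the stop date or the Ongoing box, without imputing a date, so rows 1 and 2 remain in conflict.

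**Conclusion.** The SAP is wrong as written on this point, not merely short of detail: two stated rules for one flag contradict each other, and no text says which applies. The conflict is certain when the start year is missing and the drug is ongoing (row 1). It also holds when the drug stops after the first infusion, on the natural reading of 7.2.1 (row 2). For partial dates in the year or month of the first infusion it depends on the infusion date. In the missing-year cases the 11.8 default is the weaker rule, because it can contradict what was recorded at screening.

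The primary analysis is untouched: its quantile regression has treatment as the only covariate (9.2). The exposure is confined to the ACEi/ARB subgroups, the baseline table, the ACEi/ARB use table and, conditionally, the pain medication shift table. The documents do not say how many records lack a start year. The effect is zero if there are none, so only the per-patient maximum can be stated.

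A reader might also infer that 7.2.1 should simply replace 11.8. The documents do not support that for ACEi/ARB, because the mid-month imputation fits poorly with the 4-week stability criterion.

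**What to change.** Keep one rule and cross-refer from the other section.

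1. **Missing start year.** Change the 11.8 default so that a record that is ongoing, ends after the first infusion, or was recorded at screening counts as taken at baseline, in line with 7.2.1. Keep the existing 11.8 rule that a drug ended before the first infusion is not a baseline drug. Give one stated answer for a record with neither year and Ongoing = No; 7.2.1 already has it stopped before baseline.
2. **Partial start date in the year or month of the first infusion.** State one rule based on whether the drug was recorded at screening, not on the 7.2.1 mid-period imputation alone.
3. **Scope.** Apply the rule in 7.2.1, 7.4, 8.3, 10.10 and 11.8.1; 9.6 and 10.6 then inherit it through the subgroup definition. Leave 11.8.2 as it is.

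The cost is SAP wording and one derived flag before database lock, with no new data. It assumes that the medication form identifies drugs collected at screening, as the listing flag described in 11.8 suggests. A blinded count of records with a missing start year would show whether any output changes.

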11.8.1 ACEi and ARB

The number of patients treated with ACEi (only), ARB (only) and both at Baseline and during the study (including Baseline) will be summarized using descriptive statistics by treatment group.

Usage of ACEi and/or ARB while on study will be identified based on the classification on the concomitant medication provided by investigator in the eCRF.

11.8.2 Infusion Premedication

Information on infusion premedication is collected on two different forms in the eCRF: in the concomitant medication eCRF form where the identification of medications used for that purpose is done by the classification provided by investigator. In addition, the drug administration form, collects information whether premedication was used or not in relation to each infusion (and if yes, the timing – before, during or before and during infusion).

Infusion premedication will be tabulated by treatment arm by medication class and standardized medication name. Medication classes will be presented alphabetically; within each medication class, standardized names will be sorted by decreasing order of PRX-102 frequency.

A summary table of the number (%) of patients with and without premedication use at each visit by treatment group will be derived based on the drug administration form.

A shift table, to identify how many patients changed the number of infusion premedication from baseline to Week 52 and Week 104 (or the last assessment before discontinuation) will be presented. The shift table will include the following categories: 0, 1, 2, 3+. In order to assess for each subject if any infusion premedication was used at baseline or at Week 52 or 104 or last assessment, the drug administration form at that visit will be used. If based on this form, no premedication was administered then the number of infusion premedication at that visit is 0. In case premedication administration at visit of interest is confirmed from drug administration form, the number of infusion premedication for each subject will be determined by the number of medications reported in the concomitant medications form in the eCRF, in which classification for infusion premedication is marked, and the date of the study drug infusion is within the start and end date of the premedication. Note that physician may change instructions for medication several days before the visit, so no window should be considered when comparing the dates. In case of missing or partially missing dates of infusion premedication, the following imputation rules should be considered before comparing the study drug infusion date to the medication start/end dates:

- When the start date is completely missing or the year is missing then it's assumed the medication was taken at baseline.
- When the end date is completely missing or in case the year is missing, it's assumed the medication was taken until the last visit (for patients who completed the study or terminated).
- For partially missing dates (but year is available): if month is missing then assume January for start date or December for end date. If day is missing then assume the 1st day of the month for the start date or the last day of the month for the end date.

Counting of premedication at each visit will be within medication class, namely, 0 means that the patient did not take any infusion premedication at the visit, a value of 2 means that the patients used infusion premeditations from 2 medication classes (regardless of the number of medications within a class).

A listing will be provided for infusion premeditations.

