If symptoms resolve within a single study visit and the investigator determines the symptoms were not an occurrence of progressive or severe hypersensitivity, anaphylaxis, or anaphylactoid reactions then administration of the drug may continue according to the algorithm provided above, and at the discretion of the Investigator and Medical Director.

Premedication

Premedication for subsequent PRX-102 infusions may be considered at the discretion of the investigator and Medical Director for subjects experiencing early clinical signs of hypersensitivity or rash/urticaria that responds promptly to oral antihistamine administration (see also Appendix 2 for adjustment of infusion rate). The premedication will be administered according to the following steps as needed to prevent progressive hypersensitivity:

1. Antihistamine (H1 blocker: diphenhydramine, hydroxyzine, cetirizine, loratadine, desloratidine) at a standard dose 12 hours and 2 hours before the start of the infusion.

2. H1 blocker plus H2 blocker (ranitidine, cimetidine, famotidine) at standard doses 12 hours and 2 hours before the start of the infusion.

3. H1 blocker plus H2 blocker plus prednisone up to 50 mg administered 12 hours and 2 hours before the start of the infusion.

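### The premedication shift table has no rule for a patient whose infusion form confirms premedication but who has no matching medication record, and the rule as written scores that patient 0

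*SAP*

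**What the plan says.** SAP 11.8.2 describes two sources. The drug administration form records, for each infusion, whether premedication was given and when. The concomitant medication form holds individual drugs with start and end dates, and the investigator classifies some of them as infusion premedication.

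For the shift table from baseline to Week 52 and Week 104 (or the last assessment before discontinuation), the SAP sets the following rules:

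- **Categories:** "The shift table will include the following categories: 0, 1, 2, 3", the last one being open-ended (3+). There is no category for unknown or missing.
- **Form says no:** "If based on this form, no premedication was administered then the number of infusion premedication at that visit is 0".
- **Form says yes:** "the number of infusion premedication for each subject will be determined by the number of medications reported in the concomitant medications form in the eCRF". A record counts only if it is marked as infusion premedication and "the date of the study drug infusion is within the start and end date of the premedication".
- **Tolerance on dates:** none. Because the physician may change instructions some days before the visit, the SAP says "so no window should be considered when comparing the dates".
- **Meaning of the count:** it is taken by medication class, and "0 means that the patient did not take any infusion premedication at the visit".

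The imputation rules in the same section deal with missing or partly missing dates only. SAP 7.2.1 offers no other method and points back to 11.8.2. The separate summary of patients with and without premedication at each visit is derived from the drug administration form alone.

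**The concern.** The two steps answer different questions from different forms, and the plan does not say what happens when they disagree. A patient can be a confirmed user on the infusion form and have no qualifying record on the other form. The drug may have complete dates that end before or start after the infusion, it may not be marked as infusion premedication, or it may not have been entered. The written count is then zero records, and zero is the cell that the SAP reserves for patients who took nothing.

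Infusion premedication is a listed safety measure (SAP 2.2.4). The protocol names both the ability to taper it and the overall need for it as safety variables (Protocol 8.3). The shift table is where change in that use is displayed. If confirmed users sit in the 0 cell, the table misstates change from baseline, and it can disagree with the by-visit table about who used premedication at the same visit.

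**Working it through.** The plan gives no figure to reproduce here, so the check is a trace of the counting rule followed by the weight of one patient.

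**Step 1. The rule at a single visit.** Inputs: the answer on the drug administration form, and k, the number of medication classes with a flagged record whose dates contain the infusion date (SAP 11.8.2).

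| Form | k | Count under the written rule | Agrees with the SAP's meaning of 0? | By-visit table (form alone) |
|---|---|---|---|---|
| No | any | 0 | Yes | Non-user |
| Yes | 1, 2, 3+ | k | Yes | User |
| Yes | 0 | 0 | **No** | **User** |

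The third row is the gap. The count is defined as the number of qualifying records, and nothing overrides it: there is no minimum of 1, no extra category and no date rule that applies. The imputation rules do not help, because they act only on missing or partial dates. A record with complete dates that miss the infusion day, an unflagged record and an absent record are all outside their reach.

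**Step 2. What the gap does in a shift table.** The rule is applied at baseline as well as at the later assessments. Take a patient with one class of premedication whenever it is used:

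| True shift | Unmatched at | Shift shown | Reading |
|---|---|---|---|
| 1 to 1 | later visit | 1 to 0 | Apparent stopping |
| 1 to 1 | baseline | 0 to 1 | Apparent new use |
| 1 to 1 | both | 0 to 0 | Continued use disappears |
| 1 to 0 | baseline | 0 to 0 | Real tapering hidden |
| 0 to 1 | later visit | 0 to 0 | New use hidden |

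At any one unmatched visit the count can only be too low. Across two visits the error can make premedication look more often stopped, less often stopped or newly started, depending on which visit is unmatched.

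**Step 3. Weight of one patient.** Inputs: planned arms of 52 and 26 (Protocol 10.1; SAP 3.1, which also states that 78 were randomised as planned).

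- PRX-102: 1/52 = 1.9 percentage points.
- Agalsidase beta: 1/26 = 3.8 percentage points.

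With 2:1 allocation, one such patient moves the control arm's percentages twice as far. The total effect is the number of unmatched patients times these weights. The documents give neither that number nor the rate of premedication use, so no total can be calculated.

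**The case against.** The strongest reply is that the SAP nowhere says that a confirmed user is scored 0. It assigns 0 expressly only when the form says no, and it then defines 0 as none taken. Read together, these suggest that 0 belongs to form-negative visits and that the unmatched case is simply unspecified. This is fair as far as it goes. A programmer who follows the definition would not return 0; one who follows the counting sentence would. The outcome should not depend on which sentence is programmed.

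The practical harm is also limited. Use versus non-use at each visit is reported from the form alone. Listings 16.2.3.7.1.2 and 16.2.3.7.2 show premedication and premedication by visit, so discrepancies can be traced. The eCRF has edit checks and queries (Protocol 11.2) that may catch unflagged or unentered drugs. The table is descriptive and carries no test. All of this stands and keeps the point small. It does not correct the cell in the table.

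Three stronger readings are tempting and are not supported:

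- **That the table systematically exaggerates coming off premedication.** This would follow only if mismatches occurred solely at later visits. The same rule is applied at baseline, where a mismatch works the other way.
- **That the protocol's own schedule makes mismatches likely.** Protocol Appendix 3 calls for dosing "12 hours and 2 hours before the start of the infusion". A record of the evening dose alone could miss the infusion date, but the 2-hour dose would normally fall on that date, so a record covering both doses would span it. That appendix also concerns premedication after reactions on study, whereas premedication at baseline is the patient's existing regimen (Protocol Appendix 8).
- **That the absence of a date window is itself the defect.** The SAP gives a reason for it. Accepting records from the day before could count a drug that had just been stopped or switched.

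**Conclusion.** The point holds as a small but genuine inconsistency. Applied literally, SAP 11.8.2 places a form-confirmed user with no qualifying medication record in the 0 cell, against the SAP's own meaning of 0 and against the form-based by-visit table. The net direction in Table 14.3.9.4 is unknown, and so is the frequency.

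The percentage weights assume denominators equal to the planned arm sizes; they would be slightly larger if fewer patients contribute. The conclusion also assumes that the program follows the counting sentence as written. If it set these patients to missing instead, that too would be a choice the plan does not record. The primary analysis is not touched.

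**What to change.** Add one sentence to SAP 11.8.2: when the drug administration form confirms premedication at a visit, the number is the larger of 1 and the count of matching medication classes. A separate 'used, number unknown' category would serve equally well. Either way, 0 then appears only when the form says no, and the shift table and the by-visit table agree on who was a user.

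List the visits at which the form confirms premedication and no record matches, so that their number is visible in each arm. Keep the two-source design and the no-window rule.

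The cost is one sentence, one line of program code for the count and a short listing. No new data are needed.
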